Follow-up: Up to 24 months. We will censor subjects (from the intervention) who receive a diagnosis of diabetes, when they develop a cardiovascular or cerebrovascular event, who die, or who leave the study health care systems. During each follow-up visit, the study nurse will review all prescription drugs and the RA will perform pill counts of cardiovascular drugs (we will ask subjects to bring all of their drugs in to each study visit). The study nurse will perform safety checks comparable to that during baseline evaluation. For subjects in either arm identified during our safety checks or who have events, we will recommend that they receive more intensive care from primary care physicians, cardiologists, or endocrinologists, and will message their clinicians. We will continue to monitor these subjects throughout the follow-up period albeit now on a more intensive treatment regimen.

At the end of the study, we will characterize the clinical care for subjects in both study arms, thus providing a detailed description of "usual treatment," and information about care received from other clinicians for subjects in the intervention arm. We will report on all clinicians seen (specialty, location, visit frequency and timing), conditions diagnosed and treated (psychiatric and medical), and cardiovascular conditions diagnosed and treated (major events such as ED visits or hospitalizations, diagnoses, drugs, doses). We will compile adverse events using the CATIE adverse event reporting tool as a base.^[115]

Subjects will have the option to continue coming to follow-up visits after the 12-month endpoint every 6 months for another 12 months. We will not continue to prescribe medicine to subjects in the intervention arm, rather we would continue to collect data so we can get a longer-term picture of "usual treatment" for those in each study arm (including non-randomized). RAs will perform pill counts at these additional follow-up visits, to get information about medication adherence for an additional year. NPs will continue to draw blood and ask subjects about their medications and medical history. Participants who have already signed consent and would like to participate in the post-study year of follow-up visits, will be asked to the new consent form prior to starting study procedures.

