In order to receive a bonus, Follow-Up #2 and Follow-Up #3 need to be scheduled and attended within one month after the end of the scheduling window in order to receive the bonus. If the participant completes the visit outside of the scheduling window, they will still get paid the baseline payment of \$20.00. The scheduling window refers to the two-week window within which a visit is due, which is 83 days from the prior visit. A member of the study team will contact participants to let them know when visits are due.

- If a participant completes Follow-Up #1, then staff will compensate \$40.00 for Follow-Up #2.
- If a participant completes Follow-Up #1 and Follow-Up #2, then staff will compensate \$60.00 for Follow-Up #3.
- If a participant completes Follow-Up #1 or Follow-Up #2 (but not both visits), then compensation for Follow-Up #3 will be \$40.00

V. Study Procedures

Study Site: The study will take place at four sites: McLean Hospital, BayCove Gill Clinic, Mass Mental Health Center, Edinburg Center, and Massachusetts General Hospital Outpatient Bipolar Clinic. Study procedures will be the same at each site. Study staff will bring all study equipment, including study drugs, with them to the separate sites and carry out all study procedures, leaving no burden on staff from these sites.

Contacting patient's current treater: The only information to be shared with the PCP is the "PCP letter" (included in the IRB application). This letter will be sent out between the inclusion/exclusion visit, only for patients eligible to be randomized, and the randomization visit, when we find out what arm of the study the patient is going into. Since this letter is sent prior to randomization, the letter does not include information on what study arm the patient is assigned to. The letter states that the participant will be explicitly removed from the study if requested by the PCP for medical purposes. The logic of this design is as follows: ours is a randomized open-label study. The treatment as usual arm is intended to capture naturalistic primary care of our patients while the intervention arm tests the impact of a cardiovascular preventive regimen. In these trials, "contamination" across study arms is a major concern. This refers to a process

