Data Entry: We will use several strategies to augment and evaluate the quality of data entry: 1) standardized forms, e.g., for laboratory test orders, subject interviews, and

medical record data abstraction; 2) structured data entry through a secure, serverbased database system, e.g., MS Access; 3) double entry of standardized forms with routine error checks, e.g., every third subject; and 4) automated checks for value changes across observation points, e.g., sudden increase or decrease in symptom levels – flag values for additional review.

Additional Quality Checks: We also will perform complementary quality checks: 1) routine checks for missing values; 2) cross-validation of data (e.g., psychiatric symptom levels) by comparing study data vs. medical record information for a random sample of subjects; 3) cross-validation of adherence data: (a) self-report vs. (b) RA pill counts vs. (c) medical record (plus EHR/LMR for the two Partners clinics) vs. (d) APCD pharmacy records (both study arms – includes capture of any drugs prescribed by non-psychiatrists and/or dispensed by pharmacies);[135-137] and 4) periodic trend checks to identify and confirm large changes in any outcome or covariate values. During follow-up, we will ask any subjects who forget to bring their drugs to a visit for the pill count to bring their drugs in to their next clinical appointment for a "catch up" pill count. We will use a standardized process for addressing imputation of missing values or reconciliation of different values.

VI. Biostatistical Analysis

Analysis of Aim 1: Treatment: By design, all subjects in the Intervention arm will start by being under treatment. During the course of follow-up (FU), we expect that some will stay consistently on treatment, some will discontinue treatment (become non-adherent), while others will make transitions on and off treatment in various patterns (e.g., subsequent modifications made by any PCP and/or changes in adherence over time). In contrast, by design, subjects in the Usual Treatment (control) arm do not start on treatment; however, some will initiate treatment as a result of usual clinical care, e.g., PCP initiation. For this aim, in which we study treatment use at various time points, only an intent-to-treat (ITT) approach is relevant since whether or not subjects are on treatment is the outcome itself.

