Analysis of Aim 2: ITT Effect on Cardiovascular Risk Factors: For aim 2, our primary outcome is the difference in summary risk level changes (e.g., modified Framingham score) between our two study groups, i.e., do intervention subjects experience differential changes in cardiovascular risk levels compared to control subjects. This outcome will be continuously measured (but not necessarily normally distributed).[138-140] We will also examine individual risk factor levels, including LDL, SBP, and HbA1c. By virtue of randomization and given the size of our study, the mean baseline values will be very close to equal, with the profile of the mean levels of the outcomes diverging over time. Our main analytic strategy is to use an ITT analysis, such that subjects provide data for the group to which they were randomized regardless of protocol adherence. Initially, we will get descriptive plots showing the profile of mean outcome over time in each group. This plot will be suspect if missing data (e.g., loss to follow-up) do not occur completely at random (MCAR). For more definitive analysis, we will use methods for analysis of repeated measures data that provide valid estimates of the profiles of mean outcomes over time under the weaker, missing at random (MAR) assumption that allows the probability of missing data to depend on measured characteristics. We also expect that the outcomes will be non-normally distributed based on our past experience in studying adherence. This likely bimodal adherence distribution could induce a corresponding bimodal distribution in the changes in outcome levels. All of the outcomes are likely to show this sort of non-normality. The HbA1c data also could be skewed. In general, we will therefore use analysis methods that are robust to nonnormality.

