For analysis of the repeated outcomes data, we will use econometric-style OLS linear model analysis of the repeated mean levels of the outcome over the five observation times (baseline + four follow-up times). This approach is robust to non-normal distributions. For constructing standard errors we will use cluster and heterogeneity robust estimation methods. Among estimation methods for this model, we will emphasize the use of the "fixed effects" (FE) option, which can be implemented in STATA using the xtreg command with the FE option. This essentially amounts to change score analysis that is generalized for use in situations with more than two repeated measures. This will provide estimates of the profiles of mean change from baseline in each of the treatment arms along with significance tests for contrasts between the two profiles. For plotting, the profiles of change will be anchored at the observed mean values in each arm at baseline. Inverse Probability (IP) weighting

methods will be used to account for possible endogenous loss to follow up in connection with the proposed analysis. Weighting will be based on baseline characteristics and for any given subject; the same weights will be applied to each repeated measure. We will finalize our analytic protocol before examining the outcome data, i.e., a priori delineation of the analytic protocol as is becoming the standard of analysis. We will use only marginal distributions to guide the appropriateness of the final choice of methods. Thus, we mitigate the potential for bias resulting from post-hoc choice of analysis or significance testing.

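### Aim 2 dropout weights built from baseline and held constant over visits cannot deliver the promised missing-at-random validity, and on all rows can replace one bias with another

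*Protocol*

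**What the plan says.** Protocol section VI, Analysis of Aim 2, calls for a more definitive analysis that is valid "under the weaker, missing at random (MAR) assumption that allows the probability of missing data to depend on measured characteristics". The model is OLS on five observation times with emphasis on subject fixed effects, of which the protocol says: "This essentially amounts to change score analysis that is generalized for use in situations with more than two repeated measures". Inverse-probability "methods will be used to account for possible endogenous loss to follow up in connection with the proposed analysis", and the rule for them is: "Weighting will be based on baseline characteristics and for any given subject; the same weights will be applied to each repeated measure". The text does not say whether the partial rows of dropouts are weighted or only completers, or whether arm enters the weight model.

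Post-baseline predictors of dropout are collected. Table 1 (Step 4) lists pill counts and safety checks at each quarterly visit, and Data Collection (section V) adds side effects and medication changes. Analysis of Aim 3 recognises time-varying factors; Aim 2 does not.

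Three other places bear on the point. The bonus rules under Compensation expect missed visits followed by a return: "If a participant completes Follow-Up #1 or Follow-Up #2 (but not both visits"). Follow-up (section IV) says "We will censor subjects (from the intervention) who receive a diagnosis of diabetes, when they develop a cardiovascular or cerebrovascular event", but also "We will continue to monitor these subjects throughout the follow-up period albeit now on a more intensive treatment regimen". Additional Quality Checks says only "We will use a standardized process for addressing imputation of missing values or reconciliation of different values". The SAP (02/10/2018) has no Aim 2 model and mentions inverse-probability weighting only for the medication-use outcome.

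**The concern.** The promise and the rule do not match. If measured characteristics include visit data, a baseline-only weight cannot use them. The Trial Study Design Overview reports that some intervention subjects complain of side effects and stop study drug, so loss that follows adherence or tolerability and differs by arm is plausible.

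If only baseline counts, the rule can still fail. A weight scaled to 12-month retention is also placed on early rows, where few subjects are yet missing. Subjects prone to drop out are then counted too heavily at those visits.

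At stake are the arm contrasts in LDL, SBP, HbA1c and the composite risk score, which could be biased in either direction.

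**Working it through.** **Inputs.** From the protocol: 150 per arm (Power Calculations), 1:1 allocation, baseline plus four quarterly visits. The documents give no dropout rate, dropout predictors or visit correlation, and no bias figure to reproduce. Assumed: outcome SD 1, visit correlation 0.6, 6% quarterly loss unless stated; where a drug effect is modelled, -0.8 SD while taken, 75% on drug at month 3, 10% stopping and 4% of controls starting per quarter. The true month-12 contrast is then -0.8 x (0.75 x 0.9^3 - (1 - 0.96^4)) = -0.317 SD. The standard error at 150 per arm is 0.12 to 0.14 SD.

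**Step 1: mechanism by hand.** Let p_t(x) be the chance that a subject with baseline x is observed at visit t. A row weighted by 1/p_12(x) represents baseline group x in proportion p_t(x)/p_12(x). This is 1 for everyone only at month 12. With constant quarterly loss h(x), the month-3 ratio is (1-h)^-3. Take 6% loss at the mean baseline and log-odds slope 0.7 per SD:

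- Odds at the mean: 0.06/0.94 = 0.0638.
- At +1 SD: 0.0638 x e^0.7 = 0.1285, so h = 0.114. At -1 SD: 0.0638 x e^-0.7 = 0.0317, so h = 0.031.
- Relative weight at month 3: (0.969/0.886)^3 = 1.31, where it should be 1.
- First-order shift in mean baseline: 3 x 0.7 x 0.06 = 0.126 SD. Regression to the mean turns this into -(1 - 0.6) x 0.126 = -0.050 SD of change.

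The curvature of h(x) makes the true figure larger (simulated: -0.068). Fixed effects carry part of the error to month 12.

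**Step 2: loss driven by baseline, intervention arm only.** Bias in SD:

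| Analysis | Slope 0.5 | 0.7 | 1.0 |
|---|---|---|---|
| No weights, month 12 | +0.027 | +0.037 | +0.057 |
| Planned weights by arm, all rows, month 12 | -0.025 | -0.043 | -0.078 |
| Same, month 3 | -0.042 | -0.068 | -0.128 |
| By arm, completers, month 12 | +0.001 | +0.002 | +0.002 |
| Arm omitted, all rows, month 12 | +0.028 | +0.043 | +0.072 |
| Arm omitted, completers, month 12 | +0.052 | +0.079 | +0.126 |

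The first three rows come from one run with 200,000 per arm. The last three come from a separate run on the same inputs, which gave +0.028, +0.039 and +0.058 without weights. Arm-specific, time-updated weights gave about 0. At slope 0.7 the all-rows bias is 0.043/0.128 = 0.34 SE.

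**Step 3: loss driven by post-baseline data, intervention arm only.** Month-12 bias of planned arm-specific weights:

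| Quarterly loss | All rows | Completers |
|---|---|---|
| 10% off drug v 3% on | -0.010 | -0.032 |
| 20% off drug v 3% on | -0.024 | -0.075 |
| 15% on drug v 3% off | +0.017 | +0.058 |
| Driven by prior outcome | -0.014 | -0.038 |

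In the 20% v 3% case, no weighting also gave -0.024, so the planned weights achieved nothing. In SE units this case is 0.024/0.123 = 0.20 on all rows and 0.075/0.127 = 0.59 on completers. Visit-specific weights gave about 0, but by construction, because they contain the variables that drive the loss. With missed-then-returned visits added to permanent loss, the planned weights gave -0.021 (all rows) and -0.086 (completers), and visit-specific weights -0.001.

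**Step 4: range.** With the same rule in both arms, bias (all rows/completers) was 0.000/+0.002 for baseline-driven, +0.001/0.000 for prior-outcome-driven and -0.003/-0.018 for drug-status-driven loss. With about 10% lost in each arm and slope 0.5 in one arm (correlation 0.5), all-rows bias was -0.015 at month 12 and -0.022 at month 3. The most extreme setting tried, about 40% lost after month 3 at slope 1, gave -0.36 to -0.60.

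**Step 5: where visit-specific weights fall short.** When loss follows drug status in the same quarter (20% v 3%), bias was -0.046 against -0.068 for the planned weights on all rows, so (0.068 - 0.046)/0.068 = 32% is removed. With loss before month 3 only, every method gave -0.021. When loss in one arm follows a stable subject effect (slope 0.7), unweighted fixed effects gave 0.000, planned weighted fixed effects -0.061, and visit-weighted change-score and baseline-adjusted models both -0.042.

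**The case against.** The strongest reply is that the numbers are small and assumed. Aim 2 is not the SAP's primary outcome, and its only stated target, one SD in LDL, is far above these biases. Paid attendance may keep dropout low. At month 12 the weighted and unweighted biases are about equal in size at slopes 0.5 and 0.7. The added bias needs all rows, arm-specific weights and arm-differential dropout together. Planned all-rows confidence intervals still covered 92 to 96%. At 150 per arm, a baseline-adjusted analysis with visit-specific weights carried bias of up to 0.012 SD, similar to the plan's own error in the two mildest post-baseline cases. The protocol also commits to finalising the analysis before outcomes are examined. All of this stands, and it limits the severity. It does not rescue the weighting sentence, which is a stated rule that fails its stated purpose.

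Two stronger readings are tempting, and the documents do not support either. A reader might infer that the change-score or fixed-effects model is itself an error. It is unbiased with complete data, and unweighted fixed effects is the only method compared that resists loss driven by a stable subject effect. Baseline adjustment saves variance of (1 - rho)/2 at one visit with complete data (20% at correlation 0.6), but that is an option for precision. A reader might also infer that censoring at new diabetes or a cardiovascular event deletes later Aim 2 values. The intention-to-treat rule in Analysis of Aim 2 keeps subjects in their randomised group whatever their adherence, and Follow-up keeps monitoring them. The natural reading is that the data continue.

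**Conclusion.** The concern holds for the weights. Neither reading of the rows works in both situations. On all rows, arm-specific baseline weights reverse the bias from baseline-driven loss in one arm, leave it of similar or larger size at month 12, and make it larger at early visits. On completers they remove that bias only if arm is in the weight model, and they worsen the bias from adherence-driven or prior-outcome-driven loss.

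Real size and sign cannot be known, because dropout and visit correlation are not given. Under the assumed inputs the bias is usually a fraction of one SE. It is about zero if dropout is low or follows the same baseline or prior-outcome rule in both arms. A large LDL effect would survive; smaller contrasts are the ones exposed. The change is worth making before outcomes are examined, with medium confidence about its practical effect.

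**What to change.** Replace the weighting sentence with, for example: each observed value is weighted by the inverse of the probability of being observed at that visit, estimated separately by arm from baseline and the most recent observed adherence, side effects and outcome; weights are truncated at a stated percentile; a missed visit followed by a return does not end follow-up.

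Apply these weights to a visit-by-arm regression of change from baseline with cluster-robust standard errors. Adjustment for the baseline value is optional. Name unweighted fixed effects as a sensitivity analysis, because it covers loss driven by a stable subject effect, which the visit-weighted models do not. Confirm in one line that values after a censoring event under Follow-up stay in the intention-to-treat Aim 2 analysis.

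The cost is wording and code, using data already collected at visits. The weights add some variance. They do not correct loss before month 3, most of the loss driven by events since the last visit, or loss from unrecorded causes.

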Study nurse prescribes fixed dose statin and/or ARB drugs (Intervention arm only). If subjects are randomized into the treatment arm and are already taking either a statin or any anti-hypertensive medication, they will be prescribed only the drug they are not already taking (e.g. participants on a statin will be prescribed only losartan). If subjects are already taking either a statin or anti-hypertensive medication, we will not alter the dosage of the previously prescribed medication.

We will send letters about the trial to the subject's PCP, regardless of subject's randomization.

Intervention arm subjects will get an additional blood draw in-between the medication visit and first follow-up visit to ensure it is safe for them to continue taking the study medications.

Step 4: Follow-up Visits (every 3 months for 12 months)

RAs conduct follow-up interviews, perform pill counts, and collect urine pregnancy tests (all arms)

Study nurses collect blood samples and vital signs; conduct safety checks; track visits (dates, clinician type), diagnoses, prescription drugs (names, doses, pill counts of cardiovascular drugs), and medical events (all arms)

Study nurses will record and reconcile medication lists at every visit, and note changes in medications.

Study nurse prescribes additional fixed dose statin and/or ARB drugs (Intervention arm only).

Participants who have baseline CK values within 2*ULN will be enrolled in the study. If these participants are randomized into the treatment arm, and will be receiving treatment with a statin, they will be asked to come for additional safety blood draws once per month in addition to one draw one week following the first dose of study drugs. This draws will be done to ensure participant safety while taking the study medications. If a trend of increasing CK is observed, the study medications will be discontinued (Intervention arm only).

Participants prescribed the ARB who exhibit symptoms of hypotension (e.g., syncope, dizziness) and/or have an SBP measurement of <100 mmHg at the follow-up visit will additionally be evaluated for orthostatic hypotension and tachycardia. Study PIs will be notified, and will make a decision based on these criteria to either continue or discontinue the ARB at this time. These participants will be asked to come back within one week of their follow-up visit for an additional blood pressure check. (Intervention arm only).

Step 5: Final Assessment

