The study staff will request that participants agree to have All Payers Claim Database (APCD) queried by study staff such that they may access all insurance claims made on behalf of the participant. The APCD is an excellent source of ancillary information to reconcile all patient report and medical record information. Participants will not be required to agree to have the APCD accessed in order to participate. There is a detailed data management plan that details how all data will be kept and how participant information with remain private. For secure data transmissions, we use a secure FTP, which is available through Partners Research Computing (RC). We then keep the data on our dedicated servers managed by RC, which are behind the Partners firewall. We limit data access such that only the programmer/analysts working on the project can access the data; the data remain on the servers at all time; and at no time, do any of the data leave the servers (e.g., no data on laptops, desktops, or other devices).

Blood Pressure Checks: Participants prescribed the ARB who exhibit symptoms of hypotension (e.g., syncope, dizziness) and/or have an SBP measurement of <100 mmHg at the follow-up visit will additionally be evaluated for orthostatic hypotension and

tachycardia. These participants will be asked to come back within one week for an additional blood pressure check and study PIs will be notified.

Subjects who exhibit a combination of any 2 of the 3 criteria (self-reported/observed symptoms, SBP <100 mmHg, or abnormal orthostatic measures) or all 3 criteria will be discontinued from the ARB for at least one week before coming back in for the additional safety follow-up. Study nurses will assess whether the signs/symptoms are still present, or have been alleviated after discontinuing the study drug. Study PIs will be contacted to make the decision to continue/discontinue the study drug.

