Analysis of Aim 3: Per-Protocol Effect on Cardiovascular Risk Factors: For Aim 3, we will study the same composite and individual risk factor outcomes as for Aim 2, but will estimate the per-protocol effect rather than the ITT effect. ITT is the effect of assignment to the strategies of interest; the per-protocol effect is the effect of following the strategies as indicated in the protocol and is the implicit target of inference. To estimate the per-protocol effect, however, one needs to make assumptions similar to those commonly made in the analysis of observational studies. Specifically, when adjusting for measured covariates, the valid estimation of the per-protocol effect requires that all fixed and time-varying factors that jointly predict the outcome and adherence to the assigned intervention are measured without error. We will adopt two analytic approaches, both involving adjustment via inverse probability (IP) weighting. Analysis approach 1: We will artificially censor participants when they stop adhering to the assigned strategy. We will censor subjects in the active treatment arm if/when their adherence drops below 80% of the intended dose, based on estimates of the proportion of days covered (PDC). [141-144] In sensitivity analyses, other adherence cutoff points will be used, as in our other past studies.^[145] For subjects in the control arm, we will follow two censoring strategies: (i) subjects will be censored if/when they start taking one of the drugs assigned to the active treatment arm, (ii) subjects will never be censored, which is equivalent to interpreting any treatment they receive as standard of care. We will conduct separate analyses under each of these two censoring strategies. We will compare the average outcome between arms at pre-specified time points during the follow-up. The outcome models will be similar to those described for Aim 2, but they will be fit to those remaining uncensored at the corresponding time. This approach requires no assumptions about the dose-response curve for adherence because only adherent subjects contribute to the fit of the outcome model.

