Primary study outcome: The main outcome is use of the cardiovascular prevention medications over the 12-months after study initiation. For each individual, we define the primary outcome as the proportion of the 12 follow-up months during which she/he either received any of the prescribed medication or the medication became clinically contraindicated after trial entry (as decided by the treating physician). We will assess the outcome using medication counts at each study visit (i.e., at the 3-, 6-, 9-, and 12-month study visit), supplemented by subject self-reports and the clinic chart review. For subjects who are eligible to receive both statins and ARB medications at baseline, we will calculate the number of days that they receive both medications during the 12 months of follow-up. For subjects who are eligible to receive only one of the two medications at baseline (i.e., because of pre-existing therapy with or because of contraindications to the other prevention medication before trial entry), we will calculate the number of days that they receive the medication during the 12 months of follow-up, with the same approach for addressing changes in subsequent eligibility.

Analysis of the primary study outcome: The primary analysis will follow the intention-to-treat (ITT) principle. We will use regression analysis to estimate the mean average of the primary outcome in each group and the difference between the mean outcomes, along with its 95% confidence interval and using the p-value for a null hypothesis. If clinically meaningful imbalances are detected in baseline covariates despite randomization, we will adjust for those covariates. If necessary, we will adjust for selection bias due to loss to follow-up via inverse-probability weighting. In supplemental analyses to the main ITT approach, we also will conduct appropriately adjusted per-protocol analyses. We will use STATA 13.0 for all analyses. We also will examine a number of pre-specified subgroup analyses, in which we examine whether the intervention might be more effective among those SMI patients who are more likely to receive fragmented care or less likely to be adherent to complex treatment regimens, e.g., SMI patients with Medicaid versus those with commercial health insurance.

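### Aim 3, approach 1: the 80% censoring rule has no exemption for stops the protocol itself directs, so a lasting directed stop counts as non-adherence and the estimate misses its stated target

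*Protocol*

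**What the plan says.** The protocol (VI. Biostatistical Analysis, Analysis of Aim 3) names its target: "the per-protocol effect is the effect of following the strategies as indicated in the protocol and is the implicit target of inference". Approach 1 opens with a general principle, "We will artificially censor participants when they stop adhering to the assigned strategy", and then makes it operational for the intervention arm: "We will censor subjects in the active treatment arm if/when their adherence drops below 80% of the intended dose". Adherence is measured by the proportion of days covered (PDC), and other cutoffs are planned as sensitivity analyses. The outcome models resemble those of Aim 2, but "they will be fit to those remaining uncensored at the corresponding time", and the text adds that only adherent participants inform them. Adjustment is by inverse probability weighting. The section asks that the joint predictors of outcome and adherence, fixed and time-varying, be measured without error. It lists no weight variables and does not mention positivity.

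The strategy being followed contains stops of its own:

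- Table 1, Step 4, in the paragraph on additional CK monitoring of statin recipients in the intervention arm: "If a trend of increasing CK is observed, the study medications will be discontinued".
- V. Study Procedures, Blood Pressure Checks: participants meeting at least two of three hypotension criteria "will be discontinued from the ARB for at least one week before coming back in for the additional safety follow-up". A single criterion that persists at the safety visit leads to a similar pause. In both cases the principal investigators (PIs) then decide whether the drug continues.
- VII. Risks and Discomforts: the PIs decide on stopping after an adverse event, with one example of an immediate stop.
- The design overview before Table 1: no second-line drug is offered after a medically significant reaction.

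For its primary outcome, the SAP credits time after "the medication became clinically contraindicated after trial entry". Its supplemental per-protocol analysis is mentioned without a censoring rule or a weight model.

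**The concern.** A participant taken off drug under these rules is doing what the assigned strategy prescribes. PDC does not see the reason for a gap; it counts days without drug. Unless the intended dose is redefined after a directed stop, a lasting stop takes that participant below 80% and out of the outcome model.

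Approach 1 then no longer estimates the effect it names. It estimates the effect of staying on at least 80% of the drug whatever happens, which the protocol's own safety rules do not allow. The result would rest on participants who tolerated the drug and would be reported as the effect of the strategy. The same event would also be credited in the SAP's primary outcome and treated as a departure in Aim 3.

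**Working it through.** The plan states no figure on this point, so there is none to reproduce. The checks are when a directed stop crosses the cutoff, whether weighting can repair it, and how large the gap could be.

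**1. Which directed stops cross 80%?** Visits are every 3 months, taken here as 90 days. PDC = 1 − days off / window.

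- 7 days off: 83/90 = 92.2%. 14 days: 76/90 = 84.4%. 18 days: 72/90 = 80.0%. 19 days: 71/90 = 78.9%. One- and two-week holds are not censored.
- Permanent stop at day s, perfect use before it, cumulative window: PDC at day t is s/t, which falls below 80% once t > s/0.8. For s = 90 that is after day 112.5, and for s = 180 after day 225. A stop after day 0.8 × 360 = 288 never crosses within 360 days.
- One of two drugs stopped at day s, PDC averaged over both: 12-month PDC = (1 + s/360)/2. For s = 90 this is 62.5% (censored); for s = 270 it is 87.5% (not censored).

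Early lasting stops cross. Late stops, and stops of one of two drugs, may or may not, depending on a PDC window and a two-drug rule that the protocol does not state.

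**2. Can the weights repair it?** The weight is 1/P(uncensored | history).

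- CK rule, automatic as written: once the stop has taken PDC below 80%, P(uncensored) = 0 for that history. The weight is undefined, and no other participant can stand in.
- Lasting ARB and adverse-event stops: the PIs decide, so the probability need not be zero. If the triggers (systolic pressure, symptoms, adverse events) are missing from the weight model, the result is selection bias. The weights described for loss to follow-up in Aim 2 use baseline characteristics only and would not capture these triggers.

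**3. Size.** Let p be the share stopped early under the protocol, each losing the whole drug effect D. The strategy effect is (1−p)D, and the censored analysis gives D. Relative overstatement = 1/(1−p) − 1:

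- p = 3%: 1/0.97 − 1 = 3.1%
- p = 10%: 1/0.90 − 1 = 11.1%

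If a stop loses only a fraction f of the effect because the other drug continues, the formula becomes 1/(1−pf) − 1. At p = 10% and f = 0.5 that is 1/0.95 − 1 = 5.3%. The documents give neither p nor f; all values are assumed.

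**4. Illustration by simulation (all inputs assumed).** Drug effect −30. A binary covariate present in half the arm adds 10 to the outcome and raises discretionary non-adherence from 20% to 40%. A share q has a permanent directed stop and loses the whole effect. The intervention-arm mean under the protocol is 5 − 30(1−q).

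| q | Target | Rule as written | Directed stops exempt | Share of arm represented by weights (rule as written) |
|---|---|---|---|---|
| 2% | −24.4 | −25.0 | −24.4 | 98% |
| 5% | −23.5 | −25.0 | −23.5 | 95% |
| 10% | −22.0 | −25.0 | −22.0 | 90% |
| 20% | −19.0 | −25.0 | −19.1 | 80% |

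The rule as written returns the always-on-drug mean (5 − 30 = −25) at every q. The gap is 30q: at q = 10% it is 3 against a strategy effect of 27, or 11.1%, which agrees with step 3. The largest weight was about 1.67 (1/0.6), so inspecting weights for extreme values would not reveal the problem.

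**5. Direction for systolic pressure.** Systolic pressure is both a stop trigger and an Aim 3 outcome. Censoring removes participants who are off drug, which enlarges the apparent effect. It also removes those with the lowest readings, which shrinks it. The net sign cannot be fixed from the documents.

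**The case against.** The strongest reply is that the documents nowhere say directed stops are censored. The opening principle of approach 1 speaks of ceasing to adhere to the strategy, and the intended dose, being undefined, could be read as nil once the protocol has stopped the drug. That reading is possible and may be what was meant. But the PDC rule is the only one an analyst can program, it carries no exemption, and the remark that only adherent participants feed the outcome model points to plain drug-taking. Other cutoffs do not help, because a lasting stop can cross those too.

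It can also be said that the SAP's credit for contraindicated time belongs to a medication-use endpoint, while Aim 3 concerns risk-factor levels. That is fair: the two need not match, and the SAP only shows that the principle is already accepted in one place. The protocol also expects adverse effects to be rare, so the bias may be small.

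A reader might infer more than the documents support:

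- That all of Aim 3 is affected. Approach 2 does not censor artificially.
- That any permanent stop leads to censoring. Step 1 of the working shows exceptions.
- That positivity fails for blood-pressure stops as well. The mandatory pause is at least a week, which need not cross 80%, and the lasting decision is the PIs' judgement. Even for CK, deciding what counts as a trend takes some judgement.
- That the weights become extreme. In the illustration they stayed small while part of the arm went unrepresented.

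**Conclusion.** The concern holds for approach 1 of Aim 3. As written, a lasting directed stop that takes PDC below 80% is handled as non-adherence, so the analysis estimates the effect of staying on drug and not the per-protocol effect that the section defines. Where the stop is automatic (the CK rule), weighting cannot represent those participants. Where it is a PI decision, the estimate is open to selection bias unless the triggers are in the weight model.

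The relative overstatement is 3% at an assumed early-stop share of 3% and 11% at 10%, if the whole effect is lost. It is less when one of two drugs continues, and of less certain direction for systolic pressure. The SAP's per-protocol analysis is affected only if it adopts the same rule. The point should be settled before the outcome data are examined, but it does not touch the primary ITT analysis.

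**What to change.** In approach 1, and in the SAP's supplemental per-protocol analysis if it uses the same rule:

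- Define the intended dose as the study drug the protocol currently directs for that participant.
- Compute PDC only over days on which the drug was not stopped or held under a protocol rule or a PI safety decision, and count second-line study drug as covered days.
- Do not censor such directed stops. Keep censoring discretionary ones, including changes by outside clinicians that the protocol does not direct.
- State the PDC window (cumulative or per interval) and how one- and two-drug regimens are scored.
- Put time-varying CK, systolic pressure and side-effect reports in the weight model, and report weight and positivity diagnostics, including the share of the arm that the weights represent.
- If the always-on-drug contrast is of interest, keep it as a separately labelled sensitivity analysis.

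The cost is a coded reason-for-stopping field and modest analysis work. The protocol already collects side effects and medication changes, but it describes no coded reason. No clinical stopping rule changes.
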